8.2. Critical Baseline Assessments

Subjects need to continue to meet the eligibility criteria for REM sleep behaviors:

A subject must experience frequent RBD episodes prior to Screening (Visit 1). In addition, there must be at least four (4) RBD episodes (one or more of which must include simple/major or complex RBD events) per 10 minutes of REM sleep during 1 or more qualifying night(s) based on a central review of video-PSG data obtained from the sleep laboratory during the single-blind placebo run-in period. The subject also needs to have overall AHI and REM AHI <20/hour.

8.3. Study Assessments and Procedures

8.3.1. Efficacy Assessments

All study assessments should be conducted by the investigator, and/or a suitably qualified designee, all of whom will be trained and certified to administer these measures for this study. Every effort should be made for the same person to conduct specific assessments on each individual subject at each study visit. Assessments will be monitored for quality. Screening and baseline assessments along with accompanying data will be reviewed to ensure that subjects meet the inclusion criteria. Other assessments will be monitored by using data collected.

8.3.1.1. REM Sleep Behaviors Observed with Video-Polysomnography in Sleep Lab

Whole-night video-PSG study will be performed according to the current standards. Video-PSG will provide the information on number of REM episodes, duration of REMs, and number and nature of RBD behaviors.

The video data during REM will be reviewed centrally following a methodology included in the study manual. The procedures are briefly summarized below.

An RBD behavior is defined as a motor behavior (movement) and/or vocalization with a purposeful component, seemingly expressive of a subject's mentation. Comfort moves, neck myoclonus, respiratory noises, and events related to arousals will be excluded.

The video recordings will be reviewed and analyzed to determine behaviors characteristic of RBDs. A team of expert central reviewers with specialization in sleep medicine and video analysis of motor disorders in sleep and parasomnias, appropriately trained and experienced in characterization and scoring of RBD behaviors will be assembled. The video will be analyzed independently by two of the central reviewers. All ambiguous cases (where there is discrepancy between the two reviewers' scoring) will be adjudicated by a third central reviewer. All visible movements and/or vocalizations regardless of category, severity, and duration will be analyzed. Every RBD behavior will be classified according to type of movement (movement or vocalization), topographical involvement (involvement of body parts), and presence of an associated arousal. All movements and/or vocalizations will be categorized into simple/minor, simple/major, and complex. Vocalizations (talking, crying, laughing, yelling, swearing) will also be similarly categorized.

Table 3. Classification of RBD Behavior: “The Innsbruck Scoring System”

Event Type	Description
Simple/minor movements	Small apparently involuntary movements with low amplitude
Simple/major movements	Jerks with higher movement amplitude, or intensity (e.g., whole body jerks, single limb jerk)
Complex movements	Movements showing complexity of action and involving more muscle groups simultaneously or violent movements, and can be seen as the enactment of dream contents
Simple/minor vocalizations	Unintelligible low volume vocalizations, a single word, or a small sigh
Simple/major vocalizations	Loud but short vocalizations (e.g. exclamation, or scream)
Complex vocalizations	Series of words, full sentence or parts, dialogue, singing, ranting, swearing

The frequencies of RBD behaviors will be scaled to a function of time to compute the number of RBD behaviors per 10 minutes of REM sleep.

The severity of RBD behaviors will be based on viewer ratings. Specifically, each behavior will be rated separately into one of 3 severity categories: mild, moderate, or severe.

A composite measure of both RBD behavior frequency and severity will be derived based on the weighting of each RBD behavior by its severity, with mild RBD behaviors receiving a weight of 1, moderate RBD behaviors receiving a weight of 5, and severe RBD behaviors receiving a weight of 10. The composite will then be calculated as the sum of products across all behaviors and scaled to a function of time to compute the severity-weighted RBD behaviors per 10 minutes of REM sleep.

8.3.1.2. Clinician’s Global Impression of Change – REM Sleep Behaviors

The CGIC-RBD is an ordinal scale of global evaluation which assesses the change in overall status with RBD relative to the start of treatment. The scale has only 1 item that measures global change of overall status (improvement or worsening) with RBD by the investigator on a 7-point scale from 1 to 7, where 1 = very much better and 7 = very much worse. The CGIC-RBD will be assessed in accordance with the time and events schedule described in [Table 2 \(Appendix 13.1\)](#).

8.3.1.3. Sleep Behavior-Related Injuries from the Study Diary

Sleep behavior-related injuries to the subject or the bed partner will be captured on a daily diary to be completed by the bed partner or caregiver with information provided by the subject as needed. The number of injuries to either the subject or the bed partner will be recorded.

8.3.1.4. Dramatic Dreams from the Study Diary

Dramatic dreams that are frightening, very unpleasant, and/or involve attacking or chasing scenes and their content will be captured on a daily diary to be completed by the bed partner or caregiver with information provided by the subject as needed. The number and severity of dramatic dreams will be recorded. This diary will be completed each morning at a defined time (ie, within one hour

of the time at which the diary is first completed during the study).

8.3.1.5. Scales for Outcomes of Parkinson's Disease - Sleep

SCOPA – Sleep is a validated short questionnaire that is used to assess NS problems and DS in subjects with Parkinson's disease. It takes about 10 min to complete. The NS subscale addresses NS problems in the past month and includes 5 items with 4 response options. The maximum score of this subscale is 15, with higher scores reflecting more severe sleep problems. One additional question evaluates overall sleep quality on a 7-point scale (ranging from *slept very well* to *slept very badly*). The score on this item is not included in the score of the NS scale but is used separately as a global measure of sleep quality. The DS subscale evaluates DS in the past month and includes 6 items with 4 response options, ranging from 0 (never) to 3 (often). The maximum score is 18, with higher scores reflecting more severe sleepiness ([Appendix 13.2](#)).

8.3.1.6. Visual Analog Scale for Bed Partner Sleep Quality

The bed partner's sleep quality will be assessed using a VAS, with one end of the VAS (marked with "0") representing "not able to sleep at all" and the other end of the VAS (marked with "10") representing "uninterrupted sleep". The bed partner will place an X on the scale indicating how well he/she has slept over the last 7 days. A bed partner is defined as the person who sleeps in the same bedroom as the subject ([Appendix 13.3](#)).

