3. INTRODUCTION

3.1. Background

3.1.1. Rapid Eye Movement (REM) Sleep Behavior Disorder (RBD) in Dementia with Lewy Bodies (DLB) or Parkinson's Disease Dementia (PDD)

Dementia with Lewy bodies (DLB) is a progressive neurocognitive illness characterized pathologically by the presence of diffuse clusters comprised of alpha synuclein and other proteins that aggregate in the brain and disrupt cognitive function. DLB is considered to be the second most prevalent cause of degenerative dementia in the elderly population (McKeith et al, 2004), accounting for up to 15% – 25% of dementia presentations (McKeith et al, 2000) and 15% – 20% of all autopsy confirmed dementias in old age (Mosimann and McKeith, 2003).

Parkinson's disease dementia (PDD) has pathological and clinical similarities with DLB. DLB and PDD are distinguished on the basis of sequence of symptoms: PDD patients have parkinsonism usually years before dementia; whereas DLB patients have dementia occurring before or simultaneously with parkinsonism (Aarsland et al, 2012). Between 50% and 80% of subjects with Parkinson's disease may experience dementia over the course of their illness (Alzheimer's Association, 2015). While few studies of the exact prevalence of DLB have been published, the Lewy Body Dementia Association estimates that 1.1 million individuals are affected by DLB and 0.3 million individuals are affected by PDD.

While cognitive dysfunction, manifested as deficits and fluctuation in attention is a core component of DLB and PDD, subjects also exhibit prominent behavioral disturbances early in the disease, including rapid eye movement (REM) sleep behavior disorder (RBD). RBD affects up to 80% of patients with DLB and up to 60% of patients with Parkinson's disease (Boeve et al, 2007) and is characterized by the presence of abnormal behaviors and vocalizations during the phase of sleep associated with REM and during sleep phase transitions. While individuals are normally paralyzed during REM sleep, individuals with RBD lack muscle atonia during otherwise intact REM sleep. Hence, patients exhibit violent behaviors that mirror their dream content, including screaming and running during sleep, and kicking, punching, or strangling their bed partners. Patients have limited recall of these behaviors, which are often observed only by their bed partners.

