To assess the effects of nelotanserin versus placebo on both severity and frequency of RBD behaviors (sum of simple/minor, simple/major, and complex RBD events) in the DLB patient subgroup based on video/audio assessment conducted at a sleep laboratory	The change in the composite score based on both severity and frequency of RBD behaviors (sum of simple/minor, simple/major, and complex RBD events) from baseline (V3) to EOS (V5/ET) in the DLB patient subgroup
To assess the effects of nelotanserin versus placebo on the number of injuries to the subject or bed partner in the DLB patient subgroup as recorded on the study diary completed by the subject and/or bed partner/caregiver	The change in the number of nights with injurious behaviors to the subject or bed partner per week from baseline (Week 0) to EOS (Week 4) in the DLB patient subgroup
To assess the effects of nelotanserin versus placebo on presence, frequency and severity of sleep behaviors in the DLB patient subgroup as recorded on the study diary completed by the subject and/or bed partner/caregiver	The change in the number of nights with no sleep movements and/or vocalizations per week, the nightly number of sleep movements and/or vocalizations per week, the nightly severity of sleep movements and/or vocalizations per week, and a composite score based on nightly number and severity of sleep movements and/or vocalizations per week from baseline (Week 0) to EOS (Week 4) in the DLB patient subgroup.
To assess the effects of nelotanserin versus placebo on subjective sleep quality in the DLB patient subgroup based on scores from the Scales for Outcomes in Parkinson's disease (SCOPA) – Sleep	The change in SCOPA–Nighttime Sleep (NS) problems and Daytime Sleepiness (DS) subscale scores from baseline (V4) to EOS (V5/ET) in the DLB patient subgroup
To assess the effects of nelotanserin versus placebo on quality of bed partner sleep in the DLB patient subgroup as measured by a visual analog scale (VAS) completed by the bed partner	The change in quality of bed partner sleep as measured by a VAS completed by the bed partner from baseline (V4) to EOS (V5/ET) in the DLB patient subgroup
To assess the effects of nelotanserin versus placebo on clinicians' rating of change in RBD behaviors in the DLB patient subgroup as measured by Clinicians' Global Impression of Change in RBD Behaviors (CGIC-RBD)	The comparison of CGIC-RBD at EOS (V5/ET) in the DLB patient subgroup

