Subjects will wear ActiGraph activity monitors on both of their wrists during sleep throughout the study, both at home and during the sleep laboratory nights.

Subjects and their caregivers/bedpartners will record sleep behaviors on the diary throughout the study.

A minimum of 14 days of placebo run-in is required prior to Visit 3 sleep laboratory assessments.

Visit 3 sleep laboratory assessments and confirmation of eligibility (See [Section 6.2](#)) are required prior to Visit 4 baseline/randomization.

Baseline Sleep Laboratory Visits (Visit 3 – up to 10 days)

At Visit 3, after the subject completes at least 2 weeks of placebo run-in treatment (ie, at least 14 days post Visit 2), the subject will participate in a whole-night video-PSG study at a specified sleep laboratory, during which his/her RBD behaviors will be evaluated while continuing his/her placebo treatment.

To allow subjects to acclimate to the sleep laboratory environment, subjects will spend a minimum of 2 (preferably consecutive) nights at the local sleep laboratory. During this study, the subject must have at least one qualifying night of REM sleep. A qualifying night of REM sleep is defined as a night with REM sleep duration of ≥ 10 minutes (total, not necessarily consecutive). If a subject cannot achieve one or more qualifying nights of REM sleep, the video-PSG study may be repeated for up to 2 nights as unscheduled visit(s). All sleep lab night assessments (maximum of 4 nights including unscheduled visits) must be completed within 10 days of Visit 3 (ie, first baseline sleep lab night).

The video-PSG data will be reviewed by central reviewers to determine if the subject meets the randomization criteria (See [Section 6.2](#)). During this time, the subject will continue to receive placebo until being notified to return for the next visit.

Management of patients with OSA and CSA:

During the baseline sleep laboratory visits (V3), for subjects who have overall AHI and REM AHI < 20 /hour

1. Subjects are allowed to continue in the trial if they a) per investigator's discretion, do not require initiation of treatment (eg, CPAP) and can remain untreated throughout the trial, b) need treatment adjustments and can remain on the same adjusted treatment regimen throughout the trial (eg, CPAP or alternative positive air pressure device, such as bilevel positive airway pressure or adaptive servoventilation).

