During the 4-week double-blind treatment period (Period B), investigational product will be dispensed at Visit 4 (Day 0) and will be returned at Visit 5 Clinic (Day 30) as the final study visit.

Subjects randomized to nelotanserin 80 mg will receive two (2) 20-mg nelotanserin tablets (40 mg/day) for 5 days before the dose is titrated to four (4) 20-mg nelotanserin tablets (80 mg/day) for the remainder of the double-blind period. In order to mask the treatment assignment, subjects randomized to placebo will similarly receive 2 placebo tablets for 5 days and then four (4) matching placebo tablets for the remainder of the double-blind period. A phone call should be made approximately 6 days after randomization visit to confirm up-titration occurred. Date and time of first dose taken for 80mg nelotanserin/placebo will be recorded.

Subjects will be reminded to take the blinded investigational product around the same time each evening at approximately 1 hour before bedtime. During the double-blind period, study drug dose may be reduced only once at the decrement of one or more tablets at the discretion of the investigator for safety/tolerability reasons. The study drug dose may return to 80 mg after safety/tolerability events subside. All dose adjustments must take place after a safety evaluation at the study clinic.

Phone call/Liver Function Tests (Day 14, +/- 3 days)

There will be a phone contact approximately 14 days into the double-blind period during which safety/tolerability issues with study treatment, if any, will be addressed and AEs will be collected. The site personnel will also ensure that the subject is in compliance with study drug dosing and protocol procedures, including continuing to record sleep behaviors on the diary and to wear ActiGraph activity monitors nightly at home. Laboratory samples will be taken by a visiting phlebotomist at subject's residence. The subject can make an unscheduled visit to the site or a local lab to have the lab samples drawn.

End of Study Sleep Laboratory Visits (Visit 5 on Day 28 – up to 10 days)

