At Visit 5, after the subject completes at least 28 days of double-blind treatment, the subject will participate in a whole-night video-PSG study at a specified sleep laboratory for least 2 (preferably consecutive) nights, during which his/her RBD behaviors will be evaluated. During this period, at least one qualifying night of REM sleep is required. A qualifying night of REM sleep is defined as REM sleep total duration of 10 minutes or more. There is not a requirement for number of behaviors. Subjects must remain on the study medication until it has been determined that a qualifying night of data has been collected and the final study clinic visit occurs. If a subject cannot achieve one or more qualifying nights of REM sleep, the video-PSG study may be repeated for up to 2 nights as unscheduled visit(s). All sleep lab night assessments (maximum of 4 nights including unscheduled visits) must be completed within 10 days of Visit 5 (ie, first post-randomization sleep lab night).

Subjects who discontinue study drug early during double-blind treatment and have taken at least one dose of double-blind investigational product must contact the study site personnel as soon as possible to schedule the whole-night video-PSG study.

Subjects will continue to wear ActiGraph activity monitors on both of their wrists during sleep during the double-blind period. Subjects and their caregivers/bedpartners will continue to record sleep behaviors on the diary.

Final Study Clinic Visit (Visit 5 on Day 30, + 10 days)

Subjects will return to the clinic for Visit 5 (Day 30) to complete final study assessments.

Study assessments and procedures will be performed according to [Table 2](#) below. The order of assessments should remain consistent across all clinic visits. If possible, other assessments, including ECG, vital signs, and blood draws, should be performed after cognition testing (eg, MMSE or MoCA).

Subjects who prematurely discontinue double-blind investigational product should be encouraged to return to the clinic for an Early Termination Visit and the Visit 5 assessments and procedures will be completed.

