12. If a subject discontinues due to run-in failure, the Early Termination sleep laboratory will not be required. If a subject meets discontinuation criteria during double-blind treatment, an Early Termination Visit (including sleep laboratory) will be required.
13. All subjects who are taking dopaminergic drugs (eg, levodopa, dopamine agonist) should ideally be assessed for UPDRS during their "on" state (if applicable). Record the name, dose and time of last administration of the dopaminergic drug, the subject's on/off state (if applicable), and the time of the UPDRS assessment. The timing of UPDRS assessment from last administration of dopaminergic drug should remain consistent across the study for a given subject.
14. C-SSRS Screening/Baseline version will be used at Visit 1, and C-SSRS Since Last Visit version will be used at Visit 5/ET.
15. Fasting serum samples will be collected for bile acids analysis. A minimum of 8 hours fasting is required. If the patient is unable to meet the fasting requirement, sample for the bile acids testing should not be drawn; this should be documented in the patient's records as well as the appropriate case report form. Samples will be stored and bile acid analysis may be performed if there is a liver specific safety signal or as part of a retrospective analysis.
16. Only ALT, AST, alkaline phosphatase, total and direct bilirubin will be included for chemistry samples collected at this visit, along with PT, INR and fasted bile acids. Laboratory samples will be taken by a visiting phlebotomist at subject's residence. The subject can make an unscheduled visit to the site or a local lab to have the lab samples drawn.
17. Subjects randomized to nelotanserin 80 mg/matching placebo will receive two (2) 20-mg nelotanserin/matching placebo tablets for 5 days before the dose is titrated to four (4) 20-mg nelotanserin/matching placebo tablets for the remainder of the double-blind period. A phone call should be made approximately 6 days after randomization visit to confirm up-titration occurred. Date and time of first dose taken for 80mg nelotanserin/placebo will be recorded.
18. VAS is optional if a bed partner is not available. A bed partner is defined as the person who sleeps in the same bedroom as the subject.

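### On the nominal schedule, 2 of the 7 nights rated on the end-of-study bed-partner VAS are nights the subject slept in the sleep laboratory, and no stated rule excludes them

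*Combined protocol and SAP*

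**What the plan says.** Section 8.3.1.6 gives the recall period: "The bed partner will place an X on the scale indicating how well he/she has slept over the last 7 days". The form in Appendix 13.3 likewise asks about the last week. Neither place mentions laboratory nights. Section 8.3.1.6 defines the bed partner as the person who shares the subject's bedroom.

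Section 4 lists the endpoint among the Other Secondary objectives: "The change in quality of bed partner sleep as measured by a VAS completed by the bed partner from baseline (V4) to EOS (V5/ET"). Table 2 places the VAS at Visit 2, Visit 4 and the Visit 5/early-termination clinic visit. Footnote 18 adds: "VAS is optional if a bed partner is not available".

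Section 8.1 gives the timing. The laboratory stay is headed "End of Study Sleep Laboratory Visits (Visit 5 on Day 28 – up to 10 days"). It has at least two nights, preferably consecutive, and at most four, all within 10 days of the first. The clinic visit is headed "Final Study Clinic Visit (Visit 5 on Day 30, + 10 days"). At baseline, the laboratory nights (Visit 3) start at least 14 days after Visit 2. Central review of the recordings then follows before Visit 4, with no stated turnaround time.

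**The concern.** The VAS is meant to show whether the partner sleeps better when the subject's night-time behaviors are treated. A night the subject spends in the laboratory cannot carry that information in the ordinary way, because the source of the disturbance is elsewhere. The protocol places such nights immediately before the end-of-study rating.

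If laboratory nights enter the rating alike in both arms, they pull the between-arm difference toward zero. If their number also differs between Visit 4 and Visit 5, the baseline covariate and the outcome measure different mixtures, and the change within an arm becomes hard to interpret. The loss cannot be repaired afterwards: one mark on a line cannot be split by night.

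**Working it through.** **Plan's own figure.** The protocol gives no effect size, SD or power for the VAS. Its only power statement (Section 10.2) is for the primary endpoint, and it reproduces. With N = 34 and f = 0.4, λ = N·f² = 34 × 0.16 = 5.44. On 1 and 30 degrees of freedom at two-sided 0.05 this gives power 0.617, against the stated 0.62.

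**Nominal overlap.** A rating on Day c covers nights c−7 to c−1. For c = 30 these are nights 23 to 29. The laboratory nights are 28 and 29, so the overlap is 2 of 7 (29%).

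**Overlap within the stated windows at end of study**
- Laboratory nights 28 and 29: clinic on Days 30–35 gives 2 nights, Day 36 gives 1, Days 37–40 give 0.
- Two consecutive nights with the first on Days 28–38, and clinic after the second night, from Day 30 to Day 40: 66 day pairs. Of these, 51 have 2 laboratory nights in the window, 5 have 1 and 10 have 0.
- Four consecutive nights: 45 pairs. Of these, 30 have 4, 5 have 3, 4 have 2, 3 have 1 and 3 have 0.

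**Overlap at baseline.** First laboratory night 14–24 days after Visit 2, two consecutive nights, and Visit 4 no later than day 30 after Visit 2: 110 pairs. Of these, 65 have 2 laboratory nights, 9 have 1 and 36 have 0.

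All these are counts of permitted combinations, not probabilities.

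**Effect on the comparison.** Assume the mark is an equal-weight mean of the seven nights. Let a and b be the laboratory nights in the Visit 4 and Visit 5 windows, H the partner's mean on home nights at baseline, L the mean on laboratory nights (no treatment effect), and x the true change on home nights.

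Change = [(7−b)(H+x) + bL]/7 − [(7−a)H + aL]/7 = (7−b)x/7 + (b−a)(L−H)/7.

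The second term has the same expectation in both randomized arms and drops out of the comparison. The between-arm difference is therefore multiplied by (7−b)/7:

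| Laboratory nights at Visit 5 | Share of difference kept |
|---|---|
| 0 | 7/7 = 100% |
| 2 | 5/7 = 71% |
| 3 | 4/7 = 57% |
| 4 | 3/7 = 43% |

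**Illustration only.** Borrow the primary endpoint's standardized difference of 0.8 and N = 34, and leave the SD unchanged. Two laboratory nights then give 0.8 × 5/7 = 0.571, λ = 34 × (0.571/2)² ≈ 2.78, and power 0.364 instead of 0.617. This is not an estimate for the VAS, whose effect size and SD are not given.

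**The case against.** The strongest reply is that the overlap is not fixed. The clinic visit has a window of 10 further days, and other windows are open with medical-monitor approval. A visit at least 8 days after the last laboratory night has no overlap. Early-termination ratings have no set order between laboratory and clinic. This stands: a reader might infer that every end-of-study rating includes laboratory nights, and the windows show otherwise. It does not remove the point, because Section 8.1 asks sites to keep to the schedule and the scheduled days give two nights.

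The fractions also depend on how people answer. A partner may discount the laboratory nights unprompted, or may weight the most recent nights more heavily. The documents do not say where the partner sleeps on those nights. Nights that are alike in both arms may also reduce the variance, so the loss in standardized effect may be smaller than the loss in raw difference. The four-night case needs two unscheduled repeats, which are allowed only when no night had enough REM sleep. All of this stands, and 5/7 is therefore a conditional figure.

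Finally, this is one of many endpoints in its group, and actigraphy, CGIC-RBD and SCOPA-Sleep also bear on benefit outside the laboratory. That limits the stakes, but it does not justify leaving the recall period as it is.

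**Conclusion.** The point holds for the VAS. Followed on its nominal days, the protocol has the bed partner rate a week in which 2 of 7 nights were laboratory nights for the subject, with no instruction to exclude them. The possible range is 0 to 4 nights, and the overlap at Visit 4 is uncontrolled too. Under equal weighting and no treatment effect on laboratory nights, about 71% of the between-arm difference remains in the two-night case. The direction, toward zero, assumes that overlap is similar in the two arms, as blinded randomization makes likely. The primary and key secondary analyses are unaffected.

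Two stronger readings are not supported.

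- A reader might infer that both arms will appear to improve from Visit 4 to Visit 5. That needs more laboratory nights at Visit 5 than at Visit 4, and better partner sleep on those nights. The interval from Visit 3 to Visit 4 is not stated, and partner sleep on laboratory nights is unknown. Any such shift would also cancel between arms.
- A reader might infer that the diary counts unobserved nights as symptom-free. Section 3.1.1 says of the subjects: "Patients have limited recall of these behaviors, which are often observed only by their bed partners". A bed partner is not required, and one endpoint is "The change in the number of nights with no sleep movements and/or vocalizations per week". But the diary form is not reproduced, and no text scores an unobserved night as zero. Section 10.4 sets a week to missing when fewer than half its days are reported, and leaves further detail to a SAP whose text is not in the file. Nor is the diary expressly kept on laboratory nights: Section 8.1 says "Subjects and their caregivers/bedpartners will record sleep behaviors on the diary throughout the study", whereas it names laboratory nights explicitly for the activity monitors.

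**What to change.** In Section 8.3.1.6 and Appendix 13.3, ask the bed partner to rate only those nights of the last 7 days spent at home in the same bedroom as the subject, leaving out sleep-laboratory nights. Use the same wording at Visit 4 and Visit 5/early termination. The cost is one line on the form and a rating based on fewer nights (5 instead of 7 in the nominal case).

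Alternatively, have the VAS completed just before the first laboratory night at both Visit 3 and Visit 5. This keeps a full home week at both ends. It moves the VAS time points, so Section 4 and Table 2 must be changed to match.

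A separate suggestion, not a demonstrated error: confirm that the diary offers a not-observed response and that the SAP treats it as missing, so that a night without an observer cannot count as a night without movements or vocalizations. If the option already exists, nothing changes. If it has to be added, the cost is one response option and some lost diary nights.
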